15. EFFICACY OUTCOMES

15.1. PRIMARY EFFICACY

15.1.1. PRIMARY EFFICACY VARIABLE AND DERIVATION

The primary efficacy variable is change from baseline to Day 43 in the MADRS total score. The MADRS is a 10-item checklist designed to measure the overall severity of depressive symptoms. The MADRS individual items are rated by a qualified site rater at each site on a scale of 0 to 6 in which a score of 6 represents the most severe symptoms for each item assessed. The MADRS total score is the sum of all 10 items and ranges from 0 to 60. If one or more items are missing at a visit, the total score will also be set to missing for that visit.

15.1.2. Missing Data Methods for Primary Efficacy Endpoint

The primary analysis method for evaluating the primary efficacy endpoint is the likelihood-based MMRM method described in detail in Section 15.1.3. The use of MMRM inherently implies that the treatment effect on the change from baseline in the MADRS total score will be similar for the subjects who withdraw and for those who complete the treatment in their respective treatment groups, conditional on the outcomes observed prior to withdrawal (MAR assumption), as described in section 7.1. Sensitivity analysis of the primary efficacy endpoint will be performed to evaluate the robustness of the MMRM method under different assumptions on the mechanism of missing data, as detailed in Section 15.1.4.

If a patient has the score of one or more items missing at a visit, the total score for that patient will be set to missing for that visit.

15.1.3. PRIMARY ANALYSIS OF PRIMARY EFFICACY VARIABLE

The treatment effect on the primary efficacy endpoint will be estimated using an MMRM method. The model will include the change from baseline at each pre-specified time point as the response variable, study visit, Bipolar Disorder stratification variable at screening (Bipolar I

Document: ...\ITI\ITI-007\MYA11638\Biostatistics\Documentation\SAP\ITI-007-404 SAP Final V1.0 12JUN2019.docx
Author: Version Number:1.0

Version Number 1.0

Page 24 of 53

or Bipolar II), treatment (60 mg ITI-007 or placebo) and site (or pooled site) as factors, baseline MADRS total score as covariate and interaction terms for baseline MADRS total score-by-study visit and treatment-by-study visit. The subject term will be included in the model as a random effect while all other terms will be considered fixed effects. An unstructured covariance matrix will be used to model the correlation among repeated measurements within subject.

The Kenward-Rogers method will be used to estimate the denominator degrees of freedom. The treatment and treatment-by-study visit interaction terms allow for comparisons of the treatment groups at the time point of interest (Days 8, 15, 22, 29, 36 and 43). Treatment differences will be evaluated via contrasts for the study visit-by-treatment factor.

The change from baseline to Day 43 will be used for the primary efficacy analysis, and will be performed for the ITT Set

Summary statistics for change from baseline in MADRS total score will be presented by treatment group and study visit (Day), as well as least-squares mean (LSM) estimates. standard errorsand the corresponding 95% CI for LSMs.Contrast estimates (LSM differences) for between-group comparison, the corresponding standard errors, 95% CIs, effect sizes, and p-values will also be presented for each study visit (Day). Effect size will be calculated for the ITI-007 60 mg treatment group as:

LS Mean Difference

Pooled estimate of within subject error standard deviation

15.2. **KEY SECONDARY EFFICACY ENDPOINT**

The key secondary efficacy endpoint is the change from baseline to Day 43 in the Clinical Global Impression scale, Bipolar Version, for Severity (CGI-BP-S).

The CGI-BP-S is a single value assessment of illness severity in mania, depression and overall bipolar illness and ranges from 1='Normal, not at all ill' to 7='Very severely ill' It is used in this study at screening (as a criterion for inclusion or exclusion), at baseline, and throughout the study, at Days 8, 15, 22, 29, 36, and 43. A higher score is associated with greater illness severity. The CGI-BP-S has 3 subscales, one each for mania, depression and overall bipolar illness. These 3 subscales are included in the calculation of the CGI-BP-S total score which will be recorded on the Clinical Global Impressions – Bipolar (CGI-S-BP) CRF page.

...\ITI\ITI-007\MYA11638\Biostatistics\Documentation\SAP\ITI-007-404 SAP Final V1.0 12JUN2019.docx Document: Author:

[figure not shown]
Version Number:1.0

Page 25 of 53

Change from baseline in the CGI-BP-S total score will be evaluated using an MMRM method similar to the one specified for the primary analysis of the primary efficacy endpoint, where the change from baseline to each pre-specified time point in CGI-BP-S total score is the response variable, study visit, Bipolar Disorder stratification variable at screening (Bipolar I or Bipolar II), treatment (60 mg ITI-007 or placebo) and site (or pooled site) as factors, baseline CGI-BP-S total score as covariate and interaction terms for baseline CGI-BP-S total score-by-study visit and treatment-by-study visit. The subject term will be included in the model as a random effect while all other terms will be considered as fixed effects. See Section 15.1.3, the primary analysis of primary efficacy endpoint, for more details.

Document:

...\ITI\ITI-007\MYA11638\Biostatistics\Documentation\SAP\ITI-007-404 SAP Final V1.0 12JUN2019.docx

Author:

Version Number: 1.0

Page 26 of 53

Document:

...\ITI\ITI-007\MYA11638\Biostatistics\Documentation\SAP\ITI-007-404 SAP Final V1.0 12JUN2019.docx

Author:

Version Number:1.0

Version Date: 12JUN2

STATISTICAL ANALYSIS PLAN: PROTOCOL ITI-007-404
Page 27 of 53

Document: Author: ...\ITI\ITI-007\MYA11638\Biostatistics\Documentation\SAP\ITI-007-404 SAP Final V1.0 12JUN2019.docx

or: Version Number:1.0

Version Date: 12JUN2019

Document:

...\ITI\ITI-007\MYA11638\Biostatistics\Documentation\SAP\ITI-007-404 SAP Final V1.0 12JUN2019.docx

Author:

Version Number:1.0

Version Date: 12JUN2019

[figure not shown]

Document: Author: ...\ITI\ITI-007\MYA11638\Biostatistics\Documentation\SAP\ITI-007-404 SAP Final V1.0 12JUN2019.docx

Version Number:1.0

Version Date: 12JUN2019

16. SAFETY OUTCOMES

All outputs for safety outcomes will be based on the SAF Set.

16.1. FOR BY VISIT SUMMARIES OF CHANGE FROM BASELINE SUMMARIES, THE LAST VALUE ON TREATMENT (LAST ASSESSMENT ON OR BEFORE THE LAST DOSE OF STUDY MEDICATION PLUS ONE DAY) WILL BE PRESENTED. ADVERSE EVENTS

Adverse Events (AEs) will be coded using the Medical Dictionary for Regulatory Activities

Document: ...\ITI\ITI-007\MYA11638\Biostatistics\Documentation\SAP\ITI-007-404 SAP Final V1.0 12JUN2019.docx
Author: Version Number:1.0

Version Number:1.0
Version Date: 12JUN2019

Page 31 of 53

(MedDRA) central coding dictionary currently in effect at the time of analysis or database lock.

Treatment emergent adverse events (TEAEs) are defined as AEs that started or worsened in severity on or after the first dose of study medication and on or before the date last dose of study medication plus one day.

All AEs with an onset date after the last dose of study medication plus one day will be listed in the AE data listing and labelled as 'Follow-up Adverse Event'.

See APPENDIX 2 for handling of partial or completely missing dates for AEs. In the case where it is not possible to define an AE as treatment emergent or not due to missing dates, the AE will be classified as the worst case, i.e. treatment emergent.

An overall summary of number of subjects within each of the categories described in the subsections 16.1.1 and 16.1.2 below will be provided as specified in the TLF shells.

Listings will include all AEs, TEAEs and Non-TEAEs. A seperate listing for TEAEs leading to study discontinuation will be presented.

16.1.1. AES AND TEAES

Incidence of TEAEs will be presented by System Organ Class (SOC) and Preferred Term (PT) and also broken down further by maximum severity and relationship to study medication.

The number and percentage of subjects with at least one TEAE and total number of subjects experiencing TEAEs will be summarized by PT, SOC and treatment group. A summary of TEAEs will be provided with only PTs and a separate summary for only SOCs. Additional summaries of TEAEs and TEAEs related to study medications ('possibly related', 'probably related', or 'definitely related') will be provided for PTs occurring in at least 5% of subjects in any treatment group (60 mg ITI-007 or placebo). Within each subject, multiple reports of events that mapped to a common MedDRA PT and SOC will be condensed into a single AE for incidence counts. Summaries will present SOCs in alphabetical order and PTs by descending (total) frequency within SOCs, by treatment group.

TEAEs will also be categorized according to the onset date of the TEAEs. The total number of subjects having events for each PT and SOC will be summarized by first onset categories, based on planned study visits (Day $1 - \le Day 8$, > Day $8 - \le Day 15$, > Day $15 - \le Day 22$, > Day $22 - \le Day 29$, > Day $29 - \le Day 43$).

The relative risk of at least one TEAE and for each PT and SOC will also be presented along with 95% CIs and p-values obtained by the Chi-square test for association.

AE severity is classified as "mild", "moderate", "severe", "life-threatening" by the investigator. AEs and TEAEs with a missing severity will be classified as "not specified". If a subject reports a TEAE more than once within the same PT and SOC, the event with the worst case severity will be used in the corresponding severity summaries.

Relationship to study medication, as indicated by the Investigator, is classified as "unrelated", "unlikely to be related", "possibly related", "probably related", "definitely related" (increasing severity of relationship). A "related" TEAE is defined as a TEAE "possibly related", "probably related" or "definitely related" to study medication. TEAEs with a missing relationship to study medication will be regarded as "related". If a subject reports the same AE more than once within the same PT and SOC, the AE with the worst case relationship to study medication will

Document: ...\ITI\ITI-007\MYA11638\Biostatistics\Documentation\SAP\ITI-007-404 SAP Final V1.0 12JUN2019.docx Author: Version Number:1.0

Page 32 of 53

be used in the corresponding relationship summaries. A summary of related TEAEs by SOC and PT will be presented.

AEs leading to study discontinuation will be identified by using the Completion/Withdrawal from Study page of the eCRFs, where 'Primary Reason' indicates "AE". TEAE leading to disontinuation of study medication will be identified by using the End-of-Treatment page of the eCRFs, where 'Primary Reason' indicates "AE".

For AEs leading to early study withdrawal or discontinuation of study medication, summaries of incidence rates (frequencies and percentages) by SOC and PT will be prepared.

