4 STUDY DESIGN

This is a Phase 3, randomized, double-blind, placebo-controlled, multi-center study to evaluate the efficacy and safety of lumateperone monotherapy in the treatment of patients with major depressive episodes associated with Bipolar I or Bipolar II Disorder (Bipolar Depression). The study consists of the following periods: Screening Period, double-blind On-treatment Period, and Safety Follow-up Period.

Screening Period (2 Weeks)

Potential patients will be evaluated during a Screening Period lasting up to 2 weeks, to ensure sufficient washout of restricted medications. Extension to the screening period may be approved by the Sponsor or representative in extenuating circumstances related to the patient or caregiver.

After obtaining written informed consent, diagnostic interviews and physical examinations will be conducted, vital signs and ECGs will be assessed, and blood samples for laboratory assessments will be collected. Patients considered potentially eligible for participation will be required to discontinue their current antidepressant treatment and/or other psychotropic drugs.

At baseline (Visit 2), patients who continue to meet all eligibility criteria will be randomly assigned to 1 of the 2 treatment arms for a 6-week, double-blind treatment period. Patients will be randomly assigned to 1 of the following groups: 60 mg ITI-007 or matching placebo.

Double-Blind On-Treatment Period (6 Weeks)

Patients will take their first dose of study medication the evening of their baseline visit. A single dose will be taken each day in the evening, with or without food, for the duration of the 6-week On-treatment Period.

Following randomization, patients will attend the clinic on Days 8, 15, 22, 29, 36 and 43.

Safety Follow-up Period (2 Weeks)

A return to the clinic for a safety follow-up visit will occur at Week 8, approximately 2 weeks following the last dose of study medication. If possible, patients who withdraw prematurely will be seen for an early termination visit (within 1 week of early termination) and will be asked to return to the clinic for a safety follow-up visit 2 weeks following withdrawal.

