9. DISPOSITION AND WITHDRAWALS

Subject disposition and withdrawals will be presented by treatment group, when applicable, and overall for the ENR Set.

The number and percentage of subjects who were screened, screen failed, randomized, completed or discontinued the 6-week On-Treatment Period and completed or discontinued the study, and reasons for treatment discontinuation and study discontinuation will be presented. The reasons for study withdrawal and treatment discontinuation are listed in Table B:.

The reasons for treatment discontinuation will also be presented by treatment group and by time to treatment discontinuation, categorized based on the planned visits (≤ Day 8, > Day 8 -

Document: ...\ITI\ITI-007\MYA11638\Biostatistics\Documentation\SAP\ITI-007-404 SAP Final V1.0 12JUN2019.docx Author: Version Number:1.0

Page 18 of 53

 \leq Day 15, > Day 15 - \leq Day 22, > Day 22 - \leq Day 29, > Day 29 - \leq Day 36, > Day 36 - \leq Day 43) for all subjects in the SAF Set. The reasons for study discontinuation and treatment discontinuation are listed in Table B.

A subject is defined to have completed treatment if the subject completed the 6-week On-Treatment period as recorded on the End of Treatment CRF page.

A subject is defined to have completed the study if the subject has completed the 6-week On-Treatment Period and the end of study follow-up assessments as recorded on the End of Study CRF page.

Reasons for Study Withdrawal and Study Medication Discontinuation Table B: **Terminology**

| Case Report Form Terminology | Study | Study Medication |
|---|-------|---------------------|
| Screen failure | Х | |
| Adverse event | X | Х |
| Adverse event associated with worsening of bipolar depression* | X | X |
| Adverse event not associated with worsening of bipolar depression* | X | X |
| Death | Х | Х |
| Lack of efficacy | Х | X |
| Lost to Follow-up | Х | |
| Protocol violation | Х | X |
| Physician decision | Х | X |
| Study terminated by sponsor | Х | X |
| Subject withdrew consent: | Х | X |
| Personal or family reasons; | X | X |
| Refused to provide a reason or refused all end-of-study procedures; | X | X |
| Self-reported adverse event; | X | X |
| Self-reported lack of efficacy | X | X |
| Other | Х | Х |

^{*} Adverse event associated with worsening of bipolar depression will be identified by a Medical Monitor review prior to database lock.

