14. STUDY MEDICATION EXPOSURE AND TREATMENT COMPLIANCE

Exposure to study medication and treatment compliance will be presented for the ITT and SAF Sets.

The date of first and last study medication administration will be taken from the eCRF's 'Dosing' and 'End of Treatment' forms, respectively. If a discontinued subject is missing the end of treatment date from the 'End of Treatment' form, the last known dispense date will be used as the date of last study medication administration.

Document: ...\ITI\ITI-007\MYA11638\Biostatistics\Documentation\SAP\ITI-007-404 SAP Final V1.0 12JUN2019.docx Author: Version Number:1.0

INTRA-CELLULAR THERAPIES INC. (ITCI)

STATISTICAL ANALYSIS PLAN: PROTOCOL ITI-007-404

Page 23 of 53

Duration of exposure will be summarized by treatment group as a continuous variable, using mean, SD, median, minimum and maximum. In addition, the number and percentage of subjects within each planned Study Week (1-8 days, 9-15 days, 16-22 days, 23-29 days, 30-36 days, 37-43 days, and > 43 days) will be presented.

Compliance with study medication will be derived from the drug return CRF page. For each subject, overall compliance with study medication (%) will be calculated as 100 × (Number of compliant days) / (Number of days in the On-Treatment Period), where a compliant day is defined as any day during the On-Treatment Period on which the subject took 1 capsule, and 'Number of days in the On-Treatment Period' is equivalent to 'Duration of Exposure' as defined above. The number and percentage of compliant and non compliant subjects will be presented. Non-compliant subjects are defined as those subjects with a compliance less than 80% or greater than 120%.

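### The TEAE first-onset categories skip the Day 36 visit and stop at Day 43, so the last column is twice as wide as its neighbour and late events can fall outside it

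*SAP*

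**What the plan says.** On the timing of adverse events, SAP 16.1.1 states: "The total number of subjects having events for each PT and SOC will be summarized by first onset categories, based on planned study visits". The categories it then lists are Day 1 to 8, after 8 to 15, after 15 to 22, after 22 to 29, and after 29 to 43.

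The visit schedule in Protocol section 4 is: "Following randomization, patients will attend the clinic on Days 8, 15, 22, 29, 36 and 43". SAP section 7, Table A, likewise gives Day 36 its own target day and window.

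Three other time-based summaries in the SAP do cut at Day 36:

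- SAP 9 presents reasons for treatment discontinuation by time, "categorized based on the planned visits", with separate categories for after 29 to 36 and after 36 to 43.
- SAP 13 summarizes permitted hypnotic and benzodiazepine use by week, with Days 30-36 and 37-43 separate.
- SAP 14 tabulates exposure in bands that end "23-29 days, 30-36 days, 37-43 days, and > 43 days".

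SAP 16.1 closes the TEAE window by date of onset: "on or before the date last dose of study medication plus one day".

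**The concern.** A table of first onset by time on treatment is read from left to right, to see whether events cluster early, continue steadily or appear late. That reading assumes columns of similar width. Here the final column covers two weeks and the one before it covers one, and the text asks for neither a rate nor a note on the difference. A steady onset rate would show a step up at the end, and a moderately waning rate could show a flat or rising last step.

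The table also has no place for a TEAE that starts after Day 43, although the TEAE definition and the top exposure band in SAP 14 both allow for one. What is at stake is a misreading of the late time course and a table that may not reconcile with the overall TEAE count.

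**Working it through.** **Inputs.** Category bounds are from SAP 16.1.1. The illustration uses 350 randomized 1:1 (Protocol 12.1), so 175 per arm. The documents give no TEAE onset rates and no dropout rate through Day 43, so those below are assumptions shown over a range. The plan states no figure of its own to reproduce.

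**Step 1: widths.** Width = last day − first day + 1.

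| Category | Days | Width | Share of 43 days |
|---|---|---|---|
| 1 | 1–8 | 8 | 18.6% |
| 2 | 9–15 | 7 | 16.3% |
| 3 | 16–22 | 7 | 16.3% |
| 4 | 23–29 | 7 | 16.3% |
| 5 | 30–43 | 14 | 32.6% |

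The last category is 14/7 = 2.00 times the one before it and 14/8 = 1.75 times the first.

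**Step 2: constant onset rate.** Let q be the proportion of those still at risk of a first onset who remain so after 7 days. If category 4 has expected count C, the next two weeks have qC and q²C, so

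last / previous = q + q².

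With cumulative incidence c and dropout d by Day 43, q = [(1 − c)(1 − d)]^(7/43).

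| c | d = 0 | d = 10% | d = 20% |
|---|---|---|---|
| 2% | 1.99 | 1.94 | 1.88 |
| 10% | 1.95 | 1.90 | 1.85 |
| 25% | 1.86 | 1.82 | 1.77 |
| 50% | 1.69 | 1.65 | 1.60 |

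The inflation is close to a doubling for individual preferred terms and nearer 1.6 to 1.7 for a very common row such as any TEAE.

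In counts, with 175 patients, c = 10% and no dropout:

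- As planned: 3.40, 2.92, 2.87, 2.82, **5.50**.
- With a Day 36 cut: 3.40, 2.92, 2.87, 2.82, **2.77, 2.72** (these sum to 5.50 before rounding).

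**Step 3: falling onset rate.** If the rate is multiplied by f each week and events are uncommon, the ratio is about f + f². Setting f + f² = 1 gives f = (√5 − 1)/2 = 0.618. The last count therefore exceeds the previous one for any weekly fall of less than about 38%. A day-by-day model that allows for depletion of those at risk, with a starting rate 1.5 times the constant rate of Step 2 and no dropout, gives:

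| Weekly fall | Days 23–29 | Days 30–43 as planned | Ratio | Split at Day 36 |
|---|---|---|---|---|
| 10% | 2.86 | 4.77 | 1.67 | 2.53, 2.24 |
| 20% | 1.91 | 2.71 | 1.42 | 1.51, 1.20 |
| 30% | 1.20 | 1.42 | 1.18 | 0.83, 0.58 |
| 40% | 0.70 | 0.67 | 0.96 | 0.42, 0.25 |

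A less regular pattern, with assumed weekly risks of 5, 4, 3, 2.5, 1.5 and 1.25% applied in turn to those remaining (the first category treated as one week), gives 8.75, 6.65, 4.79, 3.87, 2.26 and 1.86. Merging the last two gives 4.12 after 3.87. The fall over the first four columns is plain, and only the last step is flattened.

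**Step 4: the Day 43 end.** The first dose is on the evening of Day 1. On schedule, 42 daily doses end on Day 42, and adding one day gives Day 43, which is where the table ends. A last dose on Day 43 moves the window to Day 44, and later doses move it further. The plan leaves room for this: the last treatment visit is Day 43 ± 1 (Protocol contents, 7.8), each two-week card holds 14 doses plus 2 extras (Protocol 6.1.2), and SAP 14 has an exposure band above 43 days. Onsets on those extra days meet the TEAE definition but fit none of the five categories.

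**The case against.** The best defence is that little depends on this table. It is descriptive. The relative risks and p-values in SAP 16.1.1 are described for TEAEs overall and by PT and SOC, not by onset category. Both arms use the same bins. The bounds define the columns, so an attentive reader can see the unequal width, and recorded onset dates allow a re-cut at any time. The table shells that accompany the SAP are not among the documents and may already split the interval. All of this stands and limits the weight of the point. It does not remove the mismatch between the stated basis, planned visits, and the listed categories.

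Four stronger readings are tempting and are not supported:

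- A reader might infer that a waning pattern would vanish from the table. It would not: the first four columns still show it, and the distortion sits in the last step. At a weekly fall above about 38% even that step goes down.
- A reader might infer that the table cannot be compared with the discontinuation and exposure tables. The cuts are nested, so adding the two later columns of SAP 9, or the 30-36 and 37-43 bands of SAP 14, gives the same interval.
- A reader might infer that TEAEs after Day 43 are lost. They remain in the main incidence tables and the listings, and few patients are likely to be involved.
- A reader might infer that the absence of a denominator at risk in each interval is an error. SAP 9 plans discontinuations by interval and a figure of subjects remaining on treatment, so showing N at risk in this table is a matter of presentation.

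**Conclusion.** The point holds as a minor correction. The widths of 8, 7, 7, 7 and 14 days and the omission of Day 36 are exact from the text. The inflation of about 1.6 to 2.0 relative to the preceding week rests on a roughly constant onset rate, cumulative incidence of 2% to 50% and dropout of 0% to 20%. The flat or rising last step needs a weekly decline of less than about 38%. No onset rate in the documents says which pattern will occur.

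The gap after Day 43 follows from the SAP's own definitions. Its size cannot be computed from the documents, but it is confined to patients who dose beyond Day 42. It would be wrong to infer bias in the treatment comparison: within any category both arms cover the same days, so the unequal width does not favour either.

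**What to change.** In SAP 16.1.1, replace the last category with two: after Day 29 to Day 36, and after Day 36 to the end of the TEAE window (last dose plus one day, including Day 44 and later). The Day 36 cut then matches SAP 9, 13 and 14. The open upper end is deliberate. SAP 9 stops at Day 43 and SAP 14 has a separate band above 43 days, so neither end point can simply be copied. Bring the table shell into line if it does not already show the split.

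The cost is one line of SAP text and one extra category in the table, with smaller counts in the last two columns. Showing the number at risk at the start of each interval is optional.

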5.5.1 Reasons for Withdrawal

Patients may withdraw from the study at any time and for any reason without prejudice to their future medical care by the investigator or at the study site. Every effort should be made to keep patients in the study. The reasons for patients not completing the study will be recorded. A patient may be withdrawn from the study for any of the following reasons:

- 1. Does not meet the protocol inclusion criteria or meets the protocol exclusion criteria.
- 2. Noncompliance with the protocol.
- 3. A serious or intolerable AE that, in the investigator's opinion, requires withdrawal from the study.
- 4. Laboratory safety assessments that reveal clinically significant hematological or biochemical changes from baseline values, or baseline laboratory safety assessments that are returned after randomization but reveal clinically significant hematological or biochemical changes from screening.
- 5. Symptoms or an intercurrent illness not consistent with the protocol requirements or that justify withdrawal.
- 6. Lost to follow-up.
- 7. Other (e.g., pregnancy, development of contraindications of use of study drug).
- 8. The investigator or sponsor decide to discontinue the patient's participation in the study.
- 9. The patient withdraws consent. If consent is withdrawn, the patient must be questioned by the investigator or study site staff whether the withdrawal is due to an AE, lack of efficacy, personal or family reasons, or whether the patient withdrew consent and refused all end-of-study procedures, including refusing to give a reason; these reasons must be documented in the case report form.

The investigator will also withdraw a patient if ITI terminates the study. Upon occurrence of a serious or intolerable AE, the investigator will confer with the sponsor or Medical Monitor as the sponsor's designee. If a patient is discontinued because of an AE, the event will be followed until it is resolved, stabilizes, is determined to be non-

clinically significant, or the patient is lost to follow-up. Any patient may withdraw his or her consent at any time.

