The number and percentage of randomized subjects who discontinued due to an adverse event associated with worsening of bipolar depression will be summarized. The number and percentage of randomized subjects discontinued due to an adverse event not associated with worsening of bipolar depression will also be presented.

...\ITI\ITI-007\MYA11638\Biostatistics\Documentation\SAP\ITI-007-404 SAP Final V1.0 12JUN2019.docx Document: Author:

Version Number:1.0

INTRA-CELLULAR THERAPIES INC. (ITCI)

STATISTICAL ANALYSIS PLAN: PROTOCOL ITI-007-404

Page 19 of 53

The time to treatment discontinuation due to all reasons, adverse events, lack of efficacy, or due to any other reason of special interest will be evaluated separately using the Kaplan-Meier method. Time to treatment discontinuation of subjects in the SAF Set will be defined as the date of discontinuation minus date of first dose of study medication plus 1. Subjects who complete treatment or who discontinue for a reason other than the one being evaluated will be censored. The Log-rank test will be used to compare the time to treatment discontinuation between the 60 mg ITI-007 treatment group and placebo group. The same analysis will be repeated for time to treatment discontinuation for any reason, where only subjects who complete the 6-week Treatment Period will be censored.

The number and percentage of subjects who withdrew from the study will be summarized by visit, treatment group and overall for all subjects in the RND Set. The number of subjects randomized will also be summarized by site for the RND Set. The number of subjects remaining on treatment over time will be presented in a figure.

| The number and percentage of subjects in the RND set. | f subjects in the SAF set, the ITT set will be summarized by treatment group and overall for all |
|---|--|
| | |
| | |
| | |
| | |
| | |
| | |
| | |

Document: Author: ...\ITI\ITI-007\MYA11638\Biostatistics\Documentation\SAP\ITI-007-404 SAP Final V1.0 12JUN2019.docx Version Number:1.0

11. Demographic and other Baseline Characteristics

Demographic data and other baseline characteristics will be presented for the ITT and SAF Sets.

No formal statistical testing will be carried out for comparing demographic or other baseline characteristics between the two treatment groups.

The following demographic and other baseline characteristics will be reported:

Demographics

- o Gender
- Age (years) calculated as (Date of Informed Consent Date of Birth)/365.25

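### The AE-discontinuation tables select on primary reason AE only, so patients who withdrew consent because of a self-reported AE are left out, and SAP 9 does not say how the time-to-discontinuation analyses treat them

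*SAP*

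**What the plan says.** SAP 16.1.1 gives the selection rule for the two AE-discontinuation summaries. For study discontinuation: "AEs leading to study discontinuation will be identified by using the Completion/Withdrawal from Study page of the eCRFs, where 'Primary Reason' indicates" AE. For study medication: "TEAE leading to disontinuation of study medication will be identified by using the End-of-Treatment page of the eCRFs, where 'Primary Reason' indicates" AE. Both are then tabulated by system organ class (SOC) and preferred term (PT).

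Table B in SAP 9 lists the reasons on the case report form. Adverse event is one top-level reason. "Subject withdrew consent" is another, and "Self-reported adverse event" is one of its sub-reasons, beside self-reported lack of efficacy. Both sub-reasons are marked for study withdrawal and for study-medication discontinuation.

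SAP 9 also plans Kaplan-Meier and log-rank analyses by reason: "The time to treatment discontinuation due to all reasons, adverse events, lack of efficacy, or due to any other reason of special interest". The censoring rule is: "Subjects who complete treatment or who discontinue for a reason other than the one being evaluated will be censored". Protocol 12.4.1 has the same rule.

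On data capture, Protocol 5.5.1 says that when consent is withdrawn "the patient must be questioned by the investigator or study site staff whether the withdrawal is due to an AE" or to other causes, including lack of efficacy, and that the answer must be documented. The safety text under Protocol 12.4.4 plans to list and summarize patients who stop study or drug because of AEs, and does not limit this to a primary-reason field.

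**The concern.** Sites must find out whether an AE lies behind a withdrawal of consent, and the form has a place for the answer. The tables meant to show how many patients stopped because of AEs do not use it. Safety and tolerability are stated secondary objectives, and discontinuation due to AEs is one of the most direct tolerability measures in a six-week trial.

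The rule is also narrower than the SAP's habits elsewhere. An AE that cannot be dated is classed as treatment-emergent (16.1), a missing relationship is classed as related (16.1.1), and deaths are collected from the AE, End of Treatment and Completion/Withdrawal pages together (16.1.2). For AE discontinuation a single field decides, and the omission can only lower the count.

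If the same patients are censored in the time-to-AE analysis, they leave the risk set at the moment they stop because of an AE. That censoring is informative for the event being studied.

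**Working it through.** The documents give no AE-discontinuation rate, so there is no plan figure to reproduce. The check is a trace through the text, followed by an illustration on assumed rates.

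**1. Trace one patient.** A patient withdraws consent and, when asked as Protocol 5.5.1 requires, names an AE as the cause.
- Table B: top-level reason is consent withdrawal; sub-reason is self-reported AE.
- SAP 16.1.1 tables (study and study medication): the primary reason is not AE, so the patient is not counted. No visible text maps the sub-reason back to AE.
- SAP 9 time to discontinuation due to AEs: if reasons follow Table B's top-level headings, the patient stopped for another reason and is censored. SAP 9 does not define the AE reason and does not cite 16.1.1, so this is the literal consequence of the text, not an explicit instruction.
- SAP 9 time to discontinuation due to lack of efficacy: a self-reported lack-of-efficacy withdrawal meets the same ambiguity.
- SAP 9 any-reason analysis: only completers are censored, so the patient is an event.
- SAP 9 disposition: the patient appears under the sub-reason. Treatment-discontinuation reasons are also shown by arm and time interval in the Safety Analysis Set.
- General TEAE tables in 16.1.1: the patient's recorded TEAEs count as usual.

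The trace assumes that the primary-reason field holds Table B's top-level category. The eCRF pages are not available to confirm it.

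**2. Illustrative size (assumed rates).** Let p be the percentage with primary reason AE and q the percentage who withdraw consent for a self-reported AE. The combined rate is p + q, and the share left out is q / (p + q). Assume p = 5%.
- q = 1%: combined 6%; share left out 1/6 = 17%.
- q = 3%: combined 8%; share left out 3/8 = 38%.

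With 350 randomized 1:1 (Protocol 12.1), or 175 per arm, the counted patients are 0.05 × 175 = 8.75. Those left out are 0.01 × 175 = 1.75 to 0.03 × 175 = 5.25 per arm. The 17-38% only restates the assumed p and q.

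**3. Between-arm comparison (assumed rates).** Take AE-driven discontinuation of 8% on drug and 3% on placebo: 14.0 against 5.25 patients, risk difference 5.0 points, relative risk 8/3 = 2.67. Now record some of these as consent withdrawals.
- 25% in both arms: 6.0% against 2.25%; difference 3.75 points; relative risk 2.67.
- 50% in both arms: 4.0% against 1.5%; difference 2.5 points; relative risk 2.67.
- 50% on drug only: 4.0% against 3.0%; difference 1.0 point; relative risk 1.33.
- 50% on placebo only: 8.0% against 1.5%; difference 6.5 points; relative risk 5.33.

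Equal recording shrinks the risk difference and leaves the relative risk unchanged. Unequal recording can move the comparison either way.

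**The case against.** The strongest defence is that the split is deliberate. Protocol 5.5.1 lists an AE that in the investigator's view requires withdrawal separately from withdrawal of consent with an AE given as the cause, and Table B follows that division. Keeping investigator-judged AE withdrawals in one table and patient-attributed ones in another is coherent. The documents therefore do not make the combined rate the true one and the primary-reason rate false. This stands, and it is why both counts should be shown.

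Second, nothing is hidden. The sub-reason is in disposition, and the patient count by arm can be recovered by adding two rows. This stands for the count. It does not restore the SOC and PT breakdown or the log-rank test, which cannot be rebuilt from disposition rows. SAP 9 allows a curve for another reason of special interest but does not commit to one.

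Third, the table shells are not available, parts of the SAP are blanked out, and a mapping rule could sit there. That cannot be excluded.

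Fourth, a tick for consent withdrawal does not identify which AE, and so which preferred term, to count. This is correct, and the fix has to deal with it.

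A reader might also infer that the SAP orders these patients to be censored, that the AE dropout rate is understated, or that the rule favours the drug. The documents support none of these: the censoring follows only from a literal reading, the number of such patients is unknown, and step 3 shows that the comparison could shift in either direction.

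**Conclusion.** The point holds in a limited form. As written, SAP 16.1.1 omits consent withdrawals attributed to a self-reported AE from both AE-discontinuation tables. SAP 9 leaves their status, and that of self-reported lack-of-efficacy withdrawals, undefined in the reason-specific Kaplan-Meier analyses; the literal reading is censoring. The reported AE discontinuation rate could be lower than a combined rate by an amount the documents do not give. The figures of 5% against 6-8% are illustrative only, and the direction of any between-arm bias cannot be determined.

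The conclusion assumes that the primary-reason field holds Table B's top-level category and that no mapping rule exists in text that is not visible. The primary and key secondary endpoints are unaffected. This is a gap in tabulation and definition, not a loss of safety data, and it is worth closing because the information is already collected.

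**What to change.** In SAP 9 and 16.1.1, before unblinding:

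1. Keep the primary-reason count. Add a combined category: primary reason AE, or consent withdrawn for a self-reported AE. Define a combined lack-of-efficacy category in the same way. Report both versions as patient counts by arm.
2. State in SAP 9 how sub-reasons are assigned in the reason-specific Kaplan-Meier and log-rank analyses, and name the combined category as the event in one such analysis for AEs and one for lack of efficacy.
3. For the SOC and PT tables, include these patients through the AE record whose documented action taken (Protocol 9.4) shows that study drug was stopped. Where no record shows this, put them in a row for term not identified. The documents do not show the response options for action taken, so this should be checked against the eCRF.

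The cost is SAP wording, a derived flag and some extra programming, with no new data collection. The reported AE dropout rate may be somewhat higher, and the primary-reason row beside it shows how much of that comes from the wider definition.
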